Aim 2: To examine the effect of acute nicotine withdrawal on self-reported negative affect (anxiety, irritability) and stress reactivity, and in turn on reactivity in the amygdala and BNST. Acute nicotine withdrawal produces marked elevations in negative affect and enhanced stress reactivity. Although preclinical literature is limited, there is some evidence that these effects may be mediated by enhanced central CRF acting at the amygdala and BNST. Neuroimaging studies have linked individual differences in negative affect and stress reactivity to amygdala reactivity as well as top down regulation from the rostral ACC. Both amygdala reactivity and rACC-amygdala connectivity are in turn mediated by the short/long allele polymorphism in the 5-HTTLPR gene.

Measures: Self-reported negative affect (e.g., anxiety, irritability) and craving; BOLD response and functional connectivity during amygdala reactivity task and USCRT.

Mediators: Plasma ACTH; 5-HTTLPR short/long allelic polymorphism

Hypothesis 2.1: Compared with nicotine satiety, acute nicotine withdrawal will result in enhanced negative affect (e.g., anxiety, irritability), accompanied by enhanced amygdala and BNST reactivity. These effects will be partially mediated by an increase in plasma ACTH (as a marker of central CRF).

Hypothesis 2.2: The effect of nicotine withdrawal on amygdala reactivity will be partially mediated by reduced regulatory input from the rACC. During nicotine withdrawal we expect the rACC (and other DMN regions) to be engaged in rumination on craving and affective symptoms. Consequently, we expect reduced task-related regulatory input from the rACC to the amygdala, manifesting in reduced rACC-amygdala effective connectivity during an amygdala reactivity task.

Hypothesis 2.3: The effect of acute nicotine withdrawal on amygdala reactivity and rACC-amygdala connectivity will be most pronounced among individuals expressing the short allele of the 5-HTTLPR gene.

Hypothesis 2.4: Larger changes in amygdala and BNST reactivity will be associated with poorer treatment outcomes.

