Functional Connectivity. Seed regions for FC will be based on peak BOLD responses in ROIs for the parameter of interest. Strength of functional connectivity will be measured by correlating the BOLD time-series between seed and target regions. Fisher r to z transformations will be conducted to test for significant differences in functional connectivity strength between the non-deprived and nicotine-deprived conditions. Treatment seeking status (Treatment seeking vs non-treatment seeking) will be included as a between-subjects factor in these models to assess the main effects and of motivation to quit as well as any interaction between motivation to quit and acute nicotine withdrawal.

Correlational analyses. Bivariate partial correlations controlling for nicotine dose will also be conducted between self-report and behavioral indices of acute nicotine withdrawal and BOLD indices. Correlational analyses will serve to identify neural markers of responsivity to nicotine replacement. A series of bivariate partial correlations (controlling for nicotine dose) will also be conducted between BOLD, EEG, psychophysiological and neuroendocrine markers between nicotine-deprived and non-deprived conditions. Correlations will be conducted separately for non-treatment and treatment seeking groups.

Genotype by nicotine-deprivation interaction. 2 x 2 mixed-design ANOVAs will be conducted with genotype (short vs long allele of the 5-HTTLPR gene) varied between-subjects, and nicotine-deprivation (nicotine deprived vs non-deprived) varied within-subjects. The DVs will be BOLD signal change and functional connectivity. Treatment seeking status (Treatment seeking vs non-treatment seeking) will be included as a between-subjects factor in these models to assess the main effects and of motivation to quit as well as any interaction between motivation to quit and acute nicotine withdrawal.

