11.3. Criteria for significance

For behavioral, EEG/ERP and self-report measures alone, a statistical effect exceeding an α -level of 0.05 will be considered statistically significant. The appropriate adjustments for multiple comparison follow-up tests (e.g., Bonferroni, Tukey, Scheffe) will be employed where necessary. For the fMRI analysis, where ROIs are stipulated a priori, the threshold for statistical significance will also be set at an α -level of 0.05. For whole-brain analyses, probability thresholding of individual voxels is used in combination with minimum cluster size thresholding to increase statistical power whilst minimizing the chance of type 1 errors. The underlying principle is that true regions of activation will tend to occur over contiguous voxels whereas noise has much less of a tendency to form clusters of activated voxels. Although tables of false detection probability vs. cluster size have been published, they are limited to 2D images, and are not directly applicable; even if tables were published, they could not cover every possible combination of experimental parameters. Therefore, we empirically investigate the tradeoff between probability and cluster threshold to achieve the desired significance level for a particular experimental condition.

The AlphaSim program (within AFNI) is a Monte Carlo simulation technique that provides a method for multiple comparison correction while persevering statistical power. Using random image generation, Gaussian filtering (to simulate voxel correlations), thresholding, and tabulation of cluster size frequencies, the program generates an estimate of the overall significance level achieved for various combinations of probability and cluster size thresholds assuming spatially uncorrelated voxels. Overall, our simulations indicate that by accepting a minimum cluster size it is possible to obtain an order-of-magnitude improvement in probability threshold over the value of probability threshold required if cluster size thresholding is not used. An approximately 200-400 μ l minimum cluster size will generally be used in these studies to maintain our alpha level of 0.05. The criteria for significance (alpha) will be 0.05.

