In the current study we aim to increase the severity of nicotine-withdrawal effects by employing a 36 hour deprivation period. At the same time, individual differences in responsivity to nicotine replacement will likely reduce between-condition effects relative to smoking deprivation vs smoke adlib studies cited above. Together the above studies suggest that the weakest effects of a dose-matched nicotine vs placebo manipulation in 36 hr deprived smokers smoking deprivation manipulation will arise for behavioral measures and will be medium in size (d = 0.5). We selected a power level (1- β) of 0.80 to achieve an appropriate balance between the ability to detect significant differences and the number of participants needed. Assuming an alpha-level of 0.05, a correlation among repeated measures of r = 0.5 and a medium effect size, approximately 35 participants will be required to achieve a power of 0.80 (calculated by G*Power http://www.psycho.uniduesseldorf.de/abteilungen/aap/gpower3/).

Motivation to quit by nicotine-deprivation. To generate an estimated effect size for a 2 (treatment seeking vs non-treatment eeking) x 2 (deprived vs non-deprived) we referred to the single study conducted to date comparing treatment seeking smokers to non-treatment seeking smokers (Wilson et al., 2012). In this study, which employed self-report physiological and neuroimaging outcome measures, the smallest effect size reported for a 2 x 2 between-within interaction, where the between subjects factor was treatment seeking status, was $\eta^2 = .08$. Based on an effect size of $\eta^2 = .08$, and a power of 0.80, and an estimated correlation between repeated measures of 0.5, the required sample size to detect a true 2 x 2 between-within interaction effect is 26 individuals.

Genotype by nicotine-deprivation. To derive an estimated effect size for the genotype by nicotine-deprivation interaction we examined effects of the 5-HTTLPR polymorphism on pharmacological manipulations where conditions are varied within-subjects. Genotype by treatment effects on behavioral and self-report outcome

Principal Investigator: [name].

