measures in these studies display a small to large effect size (d = 0.30 to 0.90) (Kellner et al., 2009; Marsh et al., 2006; Thakur, Grizenko, Sengupta, Schmitz, & Joober, 2010). Recently, (Minnix et al., 2011) reported a large effect (d = 1.45) of the 5-HTTLPR polymorphism on startle reactivity in overnight deprived smokers following nicotine vs placebo nasal spray. Although the effect of the serotonin transporter polymorphism on brain (BOLD or EEG/ERP) activity changes following nicotine or smoking deprivation has yet to be investigated, large effect sizes (d > 0.80) have been reported for a smoking deprivation by COMT genotype interaction (Wang et al., 2008).

Date: March 2, 2022

Due to the large variance in reported effects we conducted two power analyses assuming a medium (d = 0.50) and large effect size (d = 0.80) effect size. Based on these analyses and assuming a correlation among repeated measures of r = 0.5, we would require approximately 16 to 35 individuals to achieve an 80% chance of detecting a genotype by nicotine-deprivation effect in the current study across our BOLD and behavioral indices (calculated by G*Power, http://www.psycho.uniduesseldorf.de/abteilungen/aap/gpower3/).

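### The 16 to 35 people quoted for the genotype-by-deprivation interaction is the cost of a plain within-person effect; if d is the genotype difference in deprivation change, d = 0.8 to 0.5 needs about 52 to 128

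*Combined protocol and SAP*

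**What the plan says.** Section 11.4 (Genotype by nicotine-deprivation) takes its effect sizes from published studies of this polymorphism. It introduces them as "Genotype by treatment effects on behavioral and self-report outcome" measures with d from 0.30 to 0.90, and adds some larger values. Because the reported effects vary so much, "we conducted two power analyses assuming a medium (d = 0.50) and large effect size (d = 0.80) effect size". Then, "assuming a correlation among repeated measures of r = 0.5", it concludes that "we would require approximately 16 to 35 individuals to achieve an 80% chance of detecting a genotype by nicotine-deprivation effect in the current study". G*Power is named as the source. The section does not say how d is defined for an interaction, how it was converted to G*Power's f, or what genotype split was assumed.

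The analysis itself is in section 11.2: "2 x 2 mixed-design ANOVAs will be conducted with genotype (short vs long allele of the 5-HTTLPR gene) varied between-subjects", with deprivation varied within subjects and treatment-seeking status added as a further between-subjects factor. Section 11.3 gives the significance level: "The criteria for significance (alpha) will be 0.05". The hypothesis served is 2.3 in section 2.3, that the effect of withdrawal on amygdala reactivity and rACC-amygdala connectivity "will be most pronounced among individuals expressing the short allele of the 5-HTTLPR gene".

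**The concern.** Section 11.4 gives about 35 people for two different questions at d = 0.5 and r = 0.5. One is whether deprivation changes the outcome in one group of smokers. The other is whether that change differs between two genotype groups. The second compares two independent groups and cannot cost the same as the first when d is the same size.

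The section's other two-group comparison points the same way. Relapsers against non-relapsers needs about 30 per group, 60 in total, at a larger d of 0.65 and with a one-tailed test.

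Hypothesis 2.3 is a named hypothesis. A reader who takes the power statement at face value could treat a null result from 35 or more people as informative evidence against an interaction of d = 0.5, when the chance of detecting it was about 30%.

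**Working it through.** **Inputs.** From 11.4: d = 0.50 and 0.80, r = 0.5, power 0.80. From 11.3: alpha 0.05. From 11.2: a 2 (genotype, between) x 2 (deprivation, within) ANOVA, whose F test is two-sided. The genotype split is not given, so 1:1 is assumed as the best case. The added treatment-seeking factor costs a few error degrees of freedom and is ignored.

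**Reproducing the plan's figure.** G*Power's default for a repeated-measures interaction uses noncentrality λ = f²·N·m/(1 − r). With m = 2 and r = 0.5 this is 4f²N.
- d = 0.5, f = 0.25: N = 34 gives λ = 4 × 0.0625 × 34 = 8.5, power 0.807.
- d = 0.8, f = 0.40: N = 16 gives λ = 4 × 0.16 × 16 = 10.24, power 0.845.

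This matches the stated 35 and 16. It is not the only route: a one-group within-subject test or a paired t test at the same d gives 34 and 15. The documents do not show which was run. All these routes charge for a within-person effect.

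**What that setting means for the interaction.** In a 2 x 2 interaction, cell-mean f = 0.25 puts the four interaction deviations at ±0.25 SD. One genotype then changes by +0.5 SD and the other by −0.5 SD, a difference of 4f = 1.0 SD. For f = 0.40 the difference is 1.6 SD. In both cases this is 2d.

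**The test at the quoted d.** The interaction F is the same test as a two-sample t test on the deprivation change score. The SD of change is SD·√(2(1 − r)), which equals the raw SD at r = 0.5, so the two scales coincide. With equal groups λ = N·d²/4.
- Check: N = 34 with a difference of 1.0 gives 34/4 = 8.5, and N = 16 with 1.6 gives 16 × 2.56/4 = 10.24. These are the values above.
- d = 0.5 needs 64 per genotype, 128 in total (λ = 128 × 0.25/4 = 8.0).
- d = 0.8 needs 26 per genotype, 52 in total (λ = 52 × 0.64/4 = 8.32).
- The stated sizes are 35/128 = 27% and 16/52 = 31% of these.
- Power with 35 people at d = 0.5 (λ = 2.19) is 0.30. Power with 16 people at d = 0.8 (λ = 2.56) is 0.32. Simulation agrees to within about 0.01.

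**Unequal genotype groups (assumed splits, not in the documents).** At d = 0.5 the total rises to about 133 at 40:60, 152 at 30:70 and 199 at 20:80.

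**Cross-check within 11.4.** Scaling the relapse comparison's 60 from d = 0.65 to 0.50 gives 60 × (0.65/0.50)² ≈ 101. The one-sided two-sample calculation at d = 0.5 gives 102.

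**Power at possible analysis sets, 1:1, two-sided.**

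| Set | N | d = 0.5 | d = 0.8 |
|---|---|---|---|
| Completers (85 + 35) | 120 | 0.78 | 0.99 |
| 80% of enrolled (162 × 0.8) | about 130 | 0.81 | 0.99 |
| All enrolled (120 + 42) | 162 | 0.89 | >0.99 |

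With 120, the smallest d reaching 80% power is 0.52 at 1:1 and 0.60 at an assumed 1:3.

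**The case against.** The strongest defence is that the figure is genuine software output and d is simply undefined. If f = 0.25 and 0.40 were intended in G*Power's default sense, 34 and 16 stand. One cited effect, d = 1.45, shows that very large values were in view. This stands in part: the fault is an effect-size definition and conversion, not a slip in calculation. It does not rescue the statement as written. The section says it assumed 0.50 and 0.80, and draws d from genotype-by-treatment effects. The default setting at f = d/2 also describes equal and opposite changes in the two genotypes, whereas Hypothesis 2.3 expects a stronger effect in one.

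A reader might also infer that the whole trial is too small for this hypothesis at d = 0.5. The documents do not support that. The 120 counts treatment seekers whose quit status is known at 1, 6 and 12 months (section 11.5), but the genotype analysis uses only the two Phase 1 scans. Enrolment is 162, and no genotype analysis set is named. At 1:1, power falls just short with 120 (0.78) and reaches 0.81 with about 130. Nor is it sound to take a further 20% off the 120: section 11.5 states that loss only for non-treatment seekers, whose 35 are already meant to be usable.

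A one-sided test would need 102 at d = 0.5, but the plan is an ANOVA F test.

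It is also fair that the polymorphism is a secondary goal (section 2.2) and that the treatment-seeking sample was sized on the relapse comparison. No enrolment number rests on 16 to 35.

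**Conclusion.** The point holds for the stated sample size and power. At the quoted effects, 16 to 35 people give about 30% power, not 80%, and the totals needed are about 52 (d = 0.8) to 128 (d = 0.5), roughly three to four times those stated.

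This rests on d being the genotype difference in the deprivation change in SD units, r = 0.5 as the plan assumes, two-sided 0.05 and equal genotype groups. Unequal groups raise the totals. If d is on the raw scale, a different r moves them as well: 178 and 72 at r = 0.3, 78 and 32 at r = 0.7.

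Whether the trial reaches 80% power at d = 0.5 depends on the analysis set and the genotype split, neither of which is stated. With the completer set it falls just short at 1:1. At d = 0.8 the planned sample is ample.

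**What to change.** In section 11.4:
- Define d for this analysis as the genotype difference in deprivation change, in SDs of the change score.
- Replace the range of 16 to 35 with about 52 to 128 for an equal split, noting that unequal groups need more.
- State the assumed genotype split, the analysis set (completers, or everyone with two usable Phase 1 scans) and the power at that N. If the set is the 120 completers, give the smallest detectable d: 0.52 at 1:1, or the value for the expected split.
- If f = 0.25 and 0.40 were truly intended, keep the numbers but say that they target genotype differences of 1.0 and 1.6 SD.

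The cost is wording only. Recruitment, procedures and the planned test do not change, but a stated figure becomes less favourable.

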11.5. Accrual number request, taking into account screening/dropouts

Treatment-seeking smokers. In the current study, an individual will be considered a completer if they meet the following criteria: 1) have completed the two pre-treatment scan visits; 2) have set a quit date; 3) attempted to quit for at least 24 hours; 4) we have been able to establish their quit status (i.e., relapsed vs non-relapse) at 1, 6 and 12 months following their last treatment visit. Based on the power analyses above we anticipate that a minimum group size of 30 in each of our two relapse groups (relapse vs abstinent) at each follow-up time point (1, 6 and 12 months) would provide a reasonable level of statistical power allowing for the detection of effects of interest in the present study. Based clinical trials of varenicline with similar follow-up time points (Aubin et al., 2008; Keating & Siddiqui, 2006; Krebs & Sherman, 2012; Swan et al., 2010a; Tsai et al., 2007), we estimate that 35% of completers at 12 months will meet criteria for 7-day point prevalent abstinence. The 12 month follow-up is the point at which we would expect our abstinent group to be smallest. Achieving a minimum of 30 abstinent smokers at 12 months would require 85 completers (i.e., 35% abstinence rate). Based on an expected 30% attrition rate at 12 months (Keating & Siddiqui, 2006) a total of 120 treatment-seeking smokers (85 completers) is therefore requested.

Non-treatment seeking smokers. An individual will be considered a completer if they complete procedures outlined for Phase 1 of the protocol (see Section 4 Study Design and Methods). Based on power analyses described above and in Section 10.4 we anticipate that 35 non-treatment seeking smokers with complete

Principal Investigator: [name].

Date: March 2, 2022

and useable data would provide a reasonable level of statistical power allowing for the detection of effects of interest in the present study. However, since acute nicotine-withdrawal effects may increase head movement and given the potential for unforeseeable errors during data collection, an estimated 20% of the participants who complete all phases of the study will likely be removed from the final analyses. Thus, a total of 42 non-treatment seeking smokers is requested.

12. Human Subjects Protection

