Principal Investigator: [name].

Protocol 12-DA-N474: Identifying neurological mechanisms that underlie acute nicotine withdrawal and drive early relapse in smokers.

Approval Date: March 2, 2022

NCT 01511614

Date: March 2, 2022

Principal Investigator: [name].

Protocol Title: Identifying neurobiological mechanisms that underlie acute nicotine withdrawal and drive early relapse in smokers.

Abbreviated Title: Neurobiology of nicotine withdrawal

Protocol Number: 12-DA-N474

Date of This Submission/Version: March 2, 2022

Principal Investigator:

T Time par in vesti	B			
Name, Degree	Branch/Institute	Bldg/Rm	Phone/Fax	Email
[name]	NIDA/IRP//NRB	BRC/07A709 [name]	P: [contact] F: [contact]	[contact]

Total requested accrual:

Total Enrollees: 577 Completers: 500

Main Study:

120 Treatment-seeking smokers (enrollees), 85 Completers

42 non-treatment seeking smokers (enrollees), 35 completers.

Motivational Interviewing Arm:

300 people interested in quitting smoking, but not yet ready to set a quit date.

Transcranial Direct Current Stimulation (tDCS) arm:

60 non-treatment seeking smokers (enrollees), 35 completers

55 nonsmokers (enrollees), 45 completers. Up to the first 25 of these enrollees will complete the tDCS without MRI (Behavioral Pilot)

Project Uses Ionizing Radiation:	¥ No	☐ Yes
IND/IDE	₩ No	□Yes
Durable Power of Attorney	₩ No	☐ Yes
Multi-institutional Project	₩ No	☐ Yes
NIDA is the coordinating site		
Data and Safety Monitoring Board	¥ No	□ Yes

Date: March 2, 2022

Principal Investigator: [name].

Technology Transfer Agreement ☐ No ☐ Yes MTA with LSU for plasma	samples. Expires Γ	December 12, 2022.	
Samples are being stored samples acquired for measurement assays have been obtained.		Yes (temporarily, page 1.25) ACTH will be destroyed once	L
Flesch-Kincaid reading level of con- (exclude boilerplate in assessing rea			

Medical Coverage Level:

Level 5 - The MAI (or designated clinician) is available by beeper or phone.

**

- **Level 1** The MAI administers all drugs and remains physically present in the experimental room during all or part of study session as determined by the Clinical Director.
- **Level 2** The MAI must be physically present in the experimental room during all or part of study session as determined by the Clinical Director.
- Level 3 The MAI must be present within the study building.
- Level 4 The MAI must be on the study campus.
- Level 5 The MAI is available by beeper or phone.

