3.1. Study population

Treatment-seeking smokers. This study will enroll healthy male and female adults who have a history of 1 or more of consistently years smoking cigarettes with a urine cotinine level corresponding to smoker status for the specific test being used, typically corresponding to a urine cotinine above about 200 ng/ml, and are actively seeking treatment for smoking cessation. We are requesting to enroll a total of 120 treatment-seeking smokers, with 85 participants expected to a) complete the two pre-treatment scan visits; 2) set a quit date; 3) attempt to quit for at least 24 hours; 4) have their quit status established (i.e., relapsed vs abstinent) at 1, 6 and 12 months following their quit date.

Non-treatment seeking smokers. This study will also recruit 42 healthy male and female adults who have a history of 1 or more years of consistently smoking cigarettes with a urine cotinine level corresponding to smoker status for the specific test being used, typically corresponding to a urine cotinine above about 200 ng/ml, but who are not currently seeking treatment for smoking cessation. 35 participants are expected to complete the two pretreatment scan visits. Non-treatment seeking smokers will not set a quit date or make a quit attempt, will not complete a treatment program as part of this study and will not be followed up after they complete the two pretreatment visits.

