4.1. Study overview

Treatment seeking smokers will be asked to complete three study phases: pre-treatment study visits, treatment visits and post-treatment follow-up visits.

Non-treatment seeking smokers will *only* be asked to complete Phase 1: Pre-treatment study visits.

PHASE 1 - Pre-treatment study visits

Phase 1 will typically require three outpatient visits to NIDA-IRP (one orientation visit, two fMRI imaging visits). Visits will take place over approximately a 3-5 week period. If an individual participant's schedule makes it difficult for them to complete the visits as they are described here, we will try to accommodate

Principal Investigator: [name].

their needs when this is possible and does not interfere with the study design or study aims. For example, orientation training day procedures could be completed over 2 or more days.

Date: March 2, 2022

The orientation visit will take approximately 6 hours and each scanning visit, approximately 9 hours. After screening and admission into the study, participants will be scheduled for an orientation visit. During this visit they will complete the informed consent process as well as task training for the scanning sessions. All participants will complete two scanning sessions: one whilst nicotine-deprived, and another non-deprived session. Nicotine deprivation will be manipulated by asking participants to either wear a dose-matched nicotine (non-deprived) or placebo (nicotine-deprived) patch during a 36 hour smoking abstinence period completed prior to both scans. The order of nicotine-deprived and non-deprived sessions will be counterbalanced across participants. Participants will be blinded as to which sessions/abstinence periods involve nicotine- or placebo-patches. The double-blind with respect to the nicotine/placebo patch condition will be maintained by [name] [name] or the protocol MAI. The investigator/s interacting with the participants will be blind to the nicotine/placebo patch condition the participant is undergoing, at the time of their interactions. "Investigator/s interacting with participants" includes the post-doc or research assistant who runs the study session and gathers research data. It does not include medical personnel such as nurses who may interact with the participant during their study visit but do not gather research data.

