11.2. Data-Analysis

Unless otherwise specified, all BOLD, genetic, behavioral, self-report and physiological data will be analyzed with AFNI or R (http://www.R-project.org; R Development Core Team, 2008). The types of statistical analysis to be utilized in the current protocol are summarized below.

Nicotine deprived vs non-deprived. Between condition (nicotine-deprived vs non-deprived) comparisons will be conducted on self-report, behavioral, BOLD ROI, resting CBF and ERP responses with a series of one-way repeated measures ANCOVAs, with nicotine-deprivation (nicotine-deprived vs non-deprived) as the within-subjects factor and nicotine dose as the covariate. By controlling for nicotine dose we can partially dissociate the

Principal Investigator: [name].

effects from acute nicotine-withdrawal effects. Treatment seeking status (Treatment seeking vs non-treatment seeking) will be included as a between-subjects factor in these models to assess the main effects and of motivation to quit as well as any interaction between motivation to quit and acute nicotine withdrawal.

Date: March 2, 2022

Mediation. Where mediation has been hypothesized (e.g., central CRF as a mediator of VS reactivity following acute nicotine withdrawal), regression coefficients for the paths of each mediation model will be derived with multiple regression and the mediation effect will be tested with ProdClin (Mackinnon, Fritz, Williams & Lockwood, 2007). ProdClin is a program developed by MacKinnon, Fritz, Williams, and Lockwood (2007) that uses the distribution of the product of paths a and b to compute asymmetric confidence intervals for the mediated effect. ProdClin is an alternative to the Sobel (1982) method that provides a more powerful and accurate test of the mediation effect because it is based on an asymmetric distribution which more closely resembles the true distribution of the product terms. Mediation models will be conducted separately for treatment-seeking and non-treatment seeking smokers.

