12.1 Subject selection

Participant recruitment will be based strictly on the inclusion/exclusion criteria. No preferences in participant recruitment will be made on the bases of gender, race, or ethnic background. Efforts will be made to avoid participant distribution bias such that if skewing is noted, subjects in the over-represented group may temporarily be excluded from the study until additional participates from under-represented groups can be established.

Efforts will be made to include ethnic minorities in proportion to their presence in the major metropolitan Baltimore area (Baltimore City, Anne Arundel, and Baltimore and Howard counties; http://quickfacts.census.gov/qfd/states/24/24510.html).

Treatment seeking smokers

	APPROVED STUDY POPULATION							
	FEMALE	MALE	TOTAL	FEMALE	MALE	TOTAL		
	ENROLLMENT ENROLLMENT ENROLLMENT COMPLETERS COMPLETER							
APPROVED CEILING	APPROVED 61 50 120 43 42 85							

NIH TARGETED/PLANNED ENROLLMENT					
	Sex/Gender				
ETHNIC CATEGORY	Females	Males	Total		
Hispanic or Latino	3	2		5**	
Not Hispanic or Latino	58	57	115		
Ethnic Category: Total of All Subjects*	61	59		120*	
RACIAL CATEGORIES					
American Indian/Alaska Native	0	0	0		
Asian	2	2	4		
Native Hawaiian or Other Pacific Islander	0	0	0		
Black or African American	39	38	77		
White	20	19	39		
Racial Categories: Total of All Subjects*	61	59		120*	

^{*}The "Ethnic Category: Total of All Subjects" must be equal to the "Racial Categories: total of All Subjects."

Non-treatment seeking smokers

APPROVED STUDY POPULATION								
	FEMALE	MALE	TOTAL	FEMALE	MALE	TOTAL		
	ENROLLMENT ENROLLMENT ENROLLMENT COMPLETERS COMPLETERS COMPLETER							
APPROVED CEILING	APPROVED 21 21 42 18 17 35							

Principal Investigator: [name].

NIH TARGETED/PL/	ANNED ENROLLMEN		
		Sex/Gender	
ETHNIC CATEGORY			
	Females	Males	Total
Hispanic or Latino	1	1	2**
Not Hispanic or Latino	20	20	40
Ethnic Category: Total of All Subjects*			42*
RACIAL CATEGORIES			
American Indian/Alaska Native	0	0	0
Asian	1	0	1
Native Hawaiian or Other Pacific Islander	0	0	0
Black or African American	13	13	26
White	7	8	15

Date: March 2, 2022

21

42*

Older individuals, defined as those over 55, will be excluded from the present study. *Justification:* Many cognitive processes change with age. In addition, the risk of difficult-to-detect medical abnormalities such as silent cerebral infarcts increases with age.

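### Section 11.5 does not deliver two sizes it states: 35 usable non-treatment seekers (28 on the plan's own counts, about 34 at best) and a minimum of 30 abstainers at 12 months (about 24 if the scan loss carries over)

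*Combined protocol and SAP*

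**What the plan says.** For non-treatment seekers, section 11.5 sets a target of 35 people with complete, usable data. Because withdrawal may increase head movement and data collection may fail, it expects that "an estimated 20% of the participants who complete all phases of the study will likely be removed from the final analyses", and it therefore requests 42. The same paragraph defines completion by procedures, not by data quality: "An individual will be considered a completer if they complete procedures outlined for Phase 1 of the protocol".

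Three other places use the same two numbers differently. The accrual list on the title page gives "42 non-treatment seeking smokers (enrollees), 35 completers". Section 3.1 says "35 participants are expected to complete the two pretreatment scan visits". The ceiling table in section 12.1 reads "APPROVED 21 21 42 18 17 35" (enrolment by sex and in total, then completers).

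For treatment seekers, section 11.5 asks for at least 30 people in each relapse group at each follow-up. It assumes 35% abstinence at 12 months: "Achieving a minimum of 30 abstinent smokers at 12 months would require 85 completers". It then allows 30% attrition and requests 120. A completer in this group must have completed both scan visits, made a quit attempt and had quit status established. Usable scan data are not a condition, and no scan loss is applied.

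Section 4.1 gives both groups the same scans: "All participants will complete two scanning sessions: one whilst nicotine-deprived, and another non-deprived session". In section 11.2, "Mediation models will be conducted separately for treatment-seeking and non-treatment seeking smokers". Section 11.4 cites 35 as the sample for 0.80 power in each mediation model.

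**The concern.** There are three faults. The 20% is added to the target instead of being divided out. The gap between 42 and 35 is used in section 11.5 for scans removed after completion and elsewhere for people who never complete, and it cannot cover both. The expected scan loss is left out for the group whose scans feed the relapse comparison.

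A reader of section 11.5 would conclude that the sample yields 35 usable non-treatment seekers and no fewer than 30 abstainers at 12 months. If it does not, the mediation models fitted in non-treatment seekers alone fall below the size the plan gives for them, and the stated relapse group size is wrong.

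**Working it through.** **Inputs.** From section 11.5: 35 usable non-treatment seekers, 20% removal, 42 requested; 85 treatment-seeking completers, 35% abstinent, 30 per relapse group. From the title page and sections 3.1 and 12.1: 42 enrolled, 35 completing. From section 11.4: d = 0.65, one-tailed alpha 0.05, power 0.80 for the relapse comparison; 35 for mediation.

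**Reproducing the plan.**
- Non-treatment seekers: 35 x (1 + 0.20) = 42, an exact match.
- Treatment seekers: 30/0.35 = 85.7 (stated 85); 85/0.70 = 121.4 (stated 120). Both agree after rounding.
- Relapse comparison: a two-sample t-test at d = 0.65, one-tailed, has power 0.800 at 30 v 30, as stated.

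**Step 1, the inflation.** The number needed before a loss of proportion p is n/(1 - p). Here 35/0.8 = 43.75, so 44 completers. With 42 completers, 42 x 0.8 = 33.6 are usable. Alone, this slip costs one or two people.

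**Step 2, the double use.** The gap is 42 - 35 = 7. If 35 complete, as three places state, and 20% of completers are then removed, 35 x 0.8 = 28 are usable. The range is 28 (stated completion) to about 34 (no non-completion), and neither end reaches 35.

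**Step 3, mediation.** Section 11.4's 35 is not met in non-treatment seekers. As an illustration only, I simulated a distribution-of-product interval with both paths 0.59, a continuous between-person predictor, no direct effect and unit residual SD. Power is about 0.81-0.82 at 35, 0.79-0.80 at 34 and 0.67-0.68 at 28. The 0.59 comes from the correlational paragraph of section 11.4; the other settings are assumptions.

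**Step 4, treatment seekers.** With no scan loss, 85 x 0.35 = 29.75 abstainers are expected, and the binomial chance of 30 or more is about 0.52. With 20% loss unrelated to relapse:
- usable: 85 x 0.8 = 68
- abstainers: 68 x 0.35 = 23.8
- relapsers: 68 x 0.65 = 44.2
- chance of 30 or more abstainers: about 0.08

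A scan loss of 5%, 10% or 15% gives 28.3, 26.8 or 25.3 abstainers.

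**Step 5, the relapse test.** One-tailed power at d = 0.65 is 0.81 at 24 v 44, against 0.88 at 30 v 55 (no scan loss) and the 0.80 planned at 30 v 30. The larger relapse group makes up for the smaller abstinent one.

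**Step 6, pooled contrasts.** Usable total: 68 + 28 = 96.

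**The case against.** Read alone, section 11.5 has one loss linking 42 and 35. If all 42 complete, about 34 are usable and the inflation slip is trivial. That is a possible reading, and it gives the upper end of the range. But it contradicts section 3.1, which says that 35 finish the scan visits, and the completer definition in section 11.5, which applies before any data are removed.

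The 20% appears only in the non-treatment paragraph, so applying it to treatment seekers is an inference. It is well supported: the wording refers to completing all phases of the study, the stated cause is withdrawal-related movement, and the scans are the same. The figure of 24 also needs removal to be independent of relapse. Section 11.5 blames withdrawal-related movement, and hypothesis 2.4 ties larger withdrawal effects to poorer outcome, so removal could fall more on relapsers and leave more than 24 abstainers. Even if all 17 removals (85 - 68) were relapsers, the expected number of abstainers would stay at 29.75.

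The mediation powers are not protocol figures. The hypothesised predictor is deprivation condition, a two-level within-person factor, which the simulation does not represent. What stands without it is that 28 is below the cited 35.

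A reader might infer that the nicotine-deprivation contrast loses power in non-treatment seekers. The documents do not support this: section 11.2 fits that contrast with treatment-seeking status as a between-subjects factor, so both groups contribute. Correlations are run separately by group, but section 11.4 asks for only 20 there, and 28 is enough.

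**Conclusion.** The point holds as a fault in stated counts, with limited consequences. On the plan's own completer count, usable non-treatment seekers number 28, and about 34 at most, against 35 stated. Of the planned analyses, only the mediation models run separately in this group are shown to fall below their stated size. This part rests on the plan's own 20% and its own definition of a completer.

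For treatment seekers, about 24 abstainers at 12 months against a minimum of 30 depends on carrying the 20% over and on removal being independent of relapse. Without either assumption, 30 is still an expected value (29.75) and not a minimum.

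A reader might go further and infer that the relapse comparison is underpowered or that enrolment must rise. The documents do not support that. The planned one-tailed test keeps 0.81 power at 24 v 44, and the pooled contrasts keep about 96 usable participants.

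**What to change.** No patients, visits or tests need to be added. The changes are to the text:

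1. In section 11.5, give non-completion and scan removal separate lines, and calculate the removal allowance by dividing by 0.8. Reconcile the 42 and 35 with the title page, section 3.1 and section 12.1.
2. Keep the enrolment of 42 and restate usable non-treatment seekers as 28 on the stated completer count (at most about 34). Say that the separate mediation models fall below the 35 cited in section 11.4. If a power is given, label it illustrative and list its assumptions.
3. Apply the scan loss to treatment seekers, stating that the 20% is carried over and assumed unrelated to relapse. Restate the 12-month groups as about 24 v 44, with one-tailed power 0.81 at d = 0.65, and describe 30 as an expected number before scan loss.
4. Note that the pooled deprivation contrasts, with about 96 usable participants, are unaffected.

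The cost is redrafting one section and reconciling the count in three other places. Some stated figures become less favourable.
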